7.4 Infusion of somatostatin

The following studies will utilize an IV infusion of the peptide hormone somatostatin, a hormone not approved by the FDA for use in humans, but commonly and safely used in human glucose metabolism research in the United States (30-36) and Europe (37-41). A modification of the glucose clamp, commonly referred to as the "pancreatic clamp," employs a short-term somatostatin infusion to suppress endogenous insulin and glucagon release while these hormones are simultaneously replaced at a prescribed infusion rate as shown in figure 2. Importantly, this approach ensures that insulin and glucagon, the key hormones influencing glucose metabolism, are equal between cohorts. This key aspect of the pancreatic clamp is essential for these metabolic studies as it allows for equal plasma levels of both insulin and glucagon between T1DM patients who are not capable of insulin secretion and non-T1DM subjects who are. Failing to equalize levels of these hormones between test subjects would confound the results considerably.

Other effects of somatostatin infusion include the inhibition of growth hormone secretion and the inhibition of gastric emptying. However, growth hormone is not known to be an acute modulator of glucose metabolism, thereby making this off-target effect of no meaningful consequence. Likewise, all subjects will be fasted while receiving the somatostatin infusion so its effect on gastric emptying will be of little consequence. We are not aware of somatostatin having been "withdrawn from the market" for any reason related to safety or effectiveness. Finally, somatostatin's short half-life (1-3 minutes, (58) the primary factor driving the development and clinical application of longer-acting synthetic analogs such as octreotide) ensures that these suppressive effects are of very short duration after the infusion is discontinued. Somatostatin used in these studies will be manufactured by Bachem Americas, Inc, in conformity with the requirements for Current Good Manufacturing Practice as specified in the International Conference on Harmonisation of Technical Requirements for Registration of Pharmaceuticals for Human Use. Testing for determination of purity and uniformity was performed by HPLC. The final drug product will be composed of 2.5 mg of somatostatin dissolved in 50 mL NS. The drug substance will be received by Vanderbilt's Investigational Drug Service (IDS) as a powder and will be compounded to obtain the IV formulation. Vanderbilt's IDS has extensive experience managing and compounding investigational agents for FDA-regulated studies and follows stringent procedures for aseptic compounding that adhere to USP<797> quidelines. The final IV formulation will be compounded by dissolving somatostatin in NS to achieve a 50 µg/mL solution. The IV formulation will be prepared sterile by utilizing a sterile, 0.2 micron filter, transferred into either sterile syringes or IV bags, and labeled as an investigational product. Filter integrity will be verified via bubble point testing as described in USP<797>. Beyond use dating for the final product will be 24 hours at controlled room temperature. A representative batch of somatostatin 4.5 mg in 50 mL NS was formulated as specified and demonstrated to be sterile. A 1 mL sample from each drug product will be sent for endotoxin testing utilizing the Kinetic Turbidimetric Assay in compliance with USP<85>. An Investigational New Drug (IND) application for the use of somatostatin in this protocol is presently under review by the FDA (# 132209).

7.5 Infusion of glucagon

Glucagon is a peptide hormone secreted by the alpha cells of the endocrine pancreas. Its effect is generally opposite that of insulin as it raises hepatic glucose production by stimulating glycogenolysis, (59) a process that raises plasma glucose levels. It is FDA approved and commonly used in the treatment of hypoglycemia.

As noted previously, glucagon will be infused into a peripheral vein at a rate chosen to approximate basal concentrations of glucagon at the liver, preventing a fall in glucagon that would otherwise occur secondary to the hyperinsulinemia and somatostatin. This allows for insulin and glucagon concentrations to be identical between test subjects, enabling a direct assessment of hepatic insulin sensitivity.

Although rapid infusions of glucagon are commonly associated with nausea and headache, our infusion rate of 0.65 ng/kg/min has been shown to maintain glucagon at a consistent, basal concentration throughout pancreatic clamp studies. (33, 38, 60) Because glucagon will remain at fasting levels throughout the study, these adverse effects are not anticipated.

While glucagon potently raises plasma glucose in the hypoglycemic state, its glucose-raising affect is attenuated in the euglycemic and hyperglycemic state. (61) For this reason and because of IV glucagon's short half-life (\approx 10 minutes), glucagon is not expected to cause iatrogenic hyperglycemia during or after the clamp study.

7.6 Special Protections for Adolescents as Research Subjects

Because adolescent subjects between ages 13-18 are included in the T1DM and MODY2 cohorts, special consideration has been given to provisions designed to protect children as outlined in 45 CFR 46, Subpart D.

7.6.1 Justification and rationale for inclusion of adolescent subjects with T1DM or MODY2

T1DM

Despite numerous advancements to reduce hyperglycemia in pediatric T1DM(62) since the publication of the groundbreaking Diabetes Control and Complications Trial in 1993,(63) macrovascular disease remains a profound contributor to excess mortality for the nearly 20,000 pediatric patients who are diagnosed with T1DM in the United States each year.(64) Among present-day adolescents with T1DM, the estimated loss in life expectancy is 11 years for males and 13 years for females compared to their non-diabetic counterparts.(65) Overall, the largest percentage in estimated loss of life expectancy was related to ischemic heart disease (36% in men, 31% in women).(65) Even contemporary T1DM patients with ideal glycemic control (indicated by an average HbA1c \leq 6.9%) remain at a 3-fold increased risk from cardiovascular disease death.(66) Thus, despite major advancements in the treatment of T1DM over the past 2 decades, the risk of death from macrovascular disease remains profoundly high.

The atherosclerotic changes of macrovascular disease (e.g. increasing carotid intima media thickness) appear to begin in childhood and adolescence(67, 68) and morbidity and mortality risk is staggeringly high in younger adults.(69) As an example, among individuals ages 1-39, the standardized mortality risk (i.e. ratio between the observed number of deaths in a study population and the number of deaths that would be expected) for ischemic heart disease death is 8.9 (95% CI 6.2–12.9) in males

and an astounding 41.7 (95% CI 28.9–58.2) in females. Thus, it is clear that pathophysiologic mechanisms that contribute to macrovascular disease *are operative early in the natural history of T1DM*. These same early pathophysiologic mechanisms have not been identified, however.

IR is a consistent(8-12) and under-recognized finding in T1DM, even among patients who lack traditional IR risk factors (such as those commonly seen in type 2 diabetes). Because IR has been strongly and independently correlated with macrovascular disease in T1DM,(14-16) an increased understanding of its root cause is needed. While earlier investigations attributed T1DM IR to hyperglycemia, (17-22) more recent studies have shown little to no correlation between hyperglycemia and insulin sensitivity.(10, 11, 13, 23) Thus, the degree to which hyperglycemia contributes to IR in T1DM is unclear, and this uncertainty suggests that other factors contribute prominently. This study tests the hypothesis that *iatrogenic hyperinsulinemia* rather than *hyperglycemia* is the primary contributor to T1DM IR. To date only one study has examined pediatric T1DM patients with typical glycemic control, which found that adolescents were 37% less insulin sensitive than matched control subjects,(11) suggesting that exposure to IR begins early in the natural history of T1DM.

To determine the root cause of T1DM IR and translate this information into therapies that would ameliorate IR in T1DM and its contribution to macrovascular disease, the mechanisms causing IR must be assessed *early in the disease duration*. This is because:

- T1DM IR appears to begin early in the disease process,(11, 17)
- the incidence of T1DM onset is highest between ages 10-14,(70) and
- 3) at younger ages and shorter disease durations there are minimal confounding covariables that would contribute to IR at a molecular level. These confounding covariables include co-morbidities associated with T1DM such as diabetic nephropathy,(71) prolonged exposure to hypertriglyceridema,(72, 73) excessive BMI(74, 75) and visceral adiposity,(76, 77), deleterious effects of aging and progressive inflammation on extracellular matrix remodeling,(78, 79) and increasing age per se.(80, 81)

By studying young patients early in the disease duration, this investigation will not only more precisely determine whether *iatrogenic hyperinsulinemia* or *hyperglycemia* is the key modifiable risk factor to address in alleviating

T1DM IR, but will simultaneously define the mechanisms causing the IR at a molecular signaling level when confounding covariables are very minimal. This knowledge is critical towards guiding subsequent therapy to mitigate IR which will considerably reduce early mortality risk from macrovascular disease in the same subjects tested in the research.

By studying younger patients early in the disease process, this investigation will minimize the confounding effect of these comorbidities and allow a more precise determination of whether *iatrogenic hyperinsulinemia* or *hyperglycemia* is the key modifiable risk factor to address in alleviating T1DM IR. With this knowledge, subsequent therapy can be directed towards mitigating IR and in so doing considerably reduce early mortality from macrovascular disease. Additionally, it will establish the presence or absence of other risk factors for macrovascular disease (e.g. dyslipidemia, endothelial dysfunction measured by peripheral artery tonometry, reduced exercise capacity) at an early point in disease duration. These data would inform subsequent longitudinal studies of macrovascular disease progression as a future direction.

MODY2

MODY2 is a less prevalent(82) form of diabetes seen in pediatrics, characterized by mild fasting hyperglycemia (110-145 mg/dL)(83) and mild chronic hyperglycemia (mean HbA1c 6.4-7.6%).(82, 84) An assessment of IR using the hyperinsulinemic, euglycemic clamp technique in this patient group has only been attempted once, was with technical limitations, and studied only one patient younger than age 18.(85) The proposed study will therefore considerably increase our knowledge of IR in MODY2 and represents the first-ever study of IR in this condition in the adolescent age group.

As with adolescent T1DM subjects, this investigation of adolescents MODY2 will determine if IR is present when other, age-related confounding covariables that might influence IR are minimized. It will also provide valuable information about the presence or absence of other macrovascular disease risk factors at a relatively early point in the natural history of the condition.

With these considerations in mind, this study proposes to test diabetic subjects in **adolescence** (ages 13-18, Tanner stage 5) and young adulthood (age 18-35).

7.6.2 Assessment of risk to adolescent participants relative to 45 CFR part 46, subpart D

Protocol Version #: 10 Protocol Date: October 24, 2017 It is our impression that T1DM and MODY2 subjects would fall under 45 CFR 46.406, as outlined in Vanderbilt's Human Research Protections Program Policy Number IX.A, section II.C. As discussed in section 7.6.1, the proposed research is likely to yield generalizable knowledge about these adolescents' condition. Specifically,

- 1. The risk represents a minor increase over minimal risk.
 - The hyperinsulinemic, euglycemic clamp has been used safely and extensively in children and adolescents elsewhere. The technique has been performed over one thousand times in healthy adolescent subjects at other institutions such as the University of Minnesota, (86-89) hundreds of times in overweight adolescent(90-92) and normal weight prepubertal subjects(93, 94) at the University of Pittsburgh, and a similar number of times in normal weight children and adolescents at the National Institutes of Health. (95, 96) Our insulin maximal infusion rate of 40 mU/m²/min is approximately equal to the rate used in studies of healthy subjects at each of these institutions and half that used in overweight subjects studied at the University of Pittsburgh.
 - As outlined in section 7.2, extensive efforts have been employed to minimize risk of hypoglycemia and hypokalemia associated with hyperinsulinemia.
 - Although use of the "pancreatic clamp technique" employed here is not used in adolescent studies at these institutions, it is commonly in adult studies elsewhere with no reported adverse effects.(30-41)
 Finally, as outlined in sections 7.4 and 7.5, every effort has been made to minimize any risks associated with the infusion of somatostatin and glucagon.
 - The study will infuse a stable isotope (deuterium) instead of a radioactive isotope (tritium) as a glucose tracer.
 - The PI has personally performed the hyperinsulinemic, euglycemic clamp over 50 times in human subjects with T2DM and a similar number of times in canine studies.
- 2. The procedure presents experiences to participants that are reasonably commensurate with those inherent in their actual or expected medical situation.
 - Hypoglycemia is a fact of life for most patients with insulin-treated diabetes. The average patient with T1DM experiences two episodes of hypoglycemia per week.(87) Every effort will be made to prevent

hypoglycemia from occurring during the clamp study at all, however.

- 3. The procedure is likely to yield generalizable knowledge about the participants' disorder or condition which is of vital importance for the understanding or amelioration of the participants' disorder or condition.
 - As previously discussed, the proposed research will provide very important information about the root cause of IR in T1DM and possibly in MODY2, which in turn contributes considerably to macrovascular disease mortality.
- 4. Adequate provisions are made for soliciting assent of the children and permission of their parents or legal guardians as detailed in the present IRB application.

The study team will discuss all procedures, risks, and benefits with potential study participants, as part of the consent/assent process. An IRB approved written informed consent/assent document will be required for participation in this study. It is understood that consent/assent is a process and not a discrete event. A participant's decision to withdraw consent/assent will be respected throughout the duration of each subject's participation in this study. It is also understood that there may be as-yet unknown or unanticipated adverse effects of this study. The study team will continually monitor for these effects and consider altering the protocol as needed to ensure patient safety. Changes in the procedures of the study, as well as any change(s) in the risks and/or benefits will be presented to and discussed with the subjects upon approval from the IRB for implementation of such revision(s), and any IRB revised written consent will be signed, as appropriate.

8.0 Reporting of Adverse Events or Unanticipated Problems involving Risk to Participants or Others

An AE will be considered to be any untoward medical occurrence in a subject, not necessarily having a causal relationship with the study. The PI will continually monitor for any AEs.

AEs will be graded according to following scale:

- 0 = No adverse events
- 1 = Mild: no limitation of usual activities, did not require treatment
- 2 = Moderate: some limitation of usual activities, resolved with or without treatment,
- 3 = Severe: inability to carry out usual activities, requiring medical intervention
- 4 = Life-threatening or disabling
- 5 = Death

Hypoglycemia and hyperglycemia will be reported as adverse events only in the case of requiring the assistance of others due to loss of consciousness or DKA. These will be considered serious adverse events (SAEs).

A member of the study team will contact each subject on the afternoon following the clamp study. Subjects who underwent a muscle biopsy will be asked to grade their pain on a 1-10 scale. Subjects taking insulin will be asked to report their 24-hour post-study glucose log numbers. The PI will continuously monitor these post-study data for hypoglycemia and alter the procedure for preventing hypoglycemia described in section 6.2.2.4 if needed.

Consistent with FDA guidelines, SAEs will be defined as any untoward medical occurrence that:

- requires inpatient hospitalization
- results in persistent or significant disability
- is suspected to cause a congenital anomaly or birth defect in a subject's unborn child
- is life-threatening
- results in death
- is considered to be an important medical event based on appropriate medical judgement (e.g. bronchospsasm requiring emergency department referral, seizures that might not result in hospitalization).

Additionally, an SAE's relationship to the study procedures will be assessed and graded as either: not related, unlikely, possible, probable, or definite.

Any AE will be assessed for whether or not it was an anticipated problem. In accordance with DHHS guidance and consistent with 45 CFR part 46, an "unanticipated problem" will include any incident, experience, or outcome that meets all of the following criteria:

- 1. unexpected (in terms of nature, severity, or frequency) given
 - a. the research procedures that are described in the protocol-related documents, including the IRB-approved research protocol and informed consent document; and
 - b. the characteristics of the subject population being studied; related or possibly related to participation in the research; and
- 2. suggests that the research places subjects or others at a greater risk of harm.
- 3. related or possibly related to participation in the research;
- 4. suggests that the research places subjects or others at a greater risk of harm than was previously known or recognized.

All unanticipated, non-serious AEs and the study team's response to the non-serious AE will be included in a report at the time of annual continuing review. The PI will review the AEs and notify the Data Safety Monitor (DSM), [name], and the IRB of any changes needed to the protocol. If needed, appropriate changes will be made to the consent form.

In accordance with IRB policy, any unanticipated SAE that is considered possibly related to participation in the study will be reported within 7 calendar days of the PI's

notification of the event to the IRB and DSM. The study team will continue to follow or obtain documentation of the resolution of any SAE.

The annual summary of all unanticipated adverse events and any audit reports will be sent to the IRB at the time of continuing review. A copy of this report will also be sent to the NIH who currently funds the PI on a K12 grant (and in the future will fund on an individual K-grant) with the Research Performance Progress Report.

Data and safety monitoring activities for this study will continue until all subjects have completed their participation and until a sufficient amount of time has passed beyond which any study-related AEs are unlikely.

This protocol will be reviewed annually (at a minimum) by the Vanderbilt IRB. The goal of this process is to determine the risks and benefits of the study in the actual experience of subjects and that measures taken to minimize risks are adequate.

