6.2.2.1 Overnight CRC stay

Subjects will be admitted to the Vanderbilt CRC on the night before the study and begin fasting except for water at 10 PM. All female subjects will have a second hCG measured to confirm the absence of pregnancy upon arrival to the CRC.

T1DM and MODY2 subjects will then be given a continuous IV infusion of regular human insulin (recombinant DNA origin), titrated by the protocol of White et al. (49) as shown in **Table 3**.

Glucose reading (mg/dL)	Insulin Infusion rate (U/h)
above 250	5
201-250	4
171-200	3
141-170	2
121-140	1.5
101-120	1
81-100	0.8
61-80	0.5
under 60	0

Table 3: Algorithm for Maintenance of OvernightEuglycemia

Glucose will be checked on an hourly basis using a calibrated, hospital bedside glucose monitor. Testing this protocol in 25 subjects with T1DM, White et al. reached and maintained near-euglycemia (101 ± 2) mg/dL) in the fasted state. Glucose fell to below 60 mg/dL on six occasions and to below 50 mg/dL on only one occasion. T1DM and MODY2 study patients should be at euglycemia when the clamp study begins (matching them with non-diabetic controls) and the overnight-titrated fasting insulin infusion rate should approximate the peripheral insulin infusion rate needed for euglycemia in each patient. Should glucose fall to < 75 mg/dL the PI may elect to infuse a small dose of 20% dextrose to prevent hypoglycemia. Should glucose fall to < 55 mg/dL and the patient experience symptoms of hypoglycemia, 20% dextrose will be at bedside to treat the hypoglycemia (e.g. 75 mL of 20% dextrose delivers 15 gm of glucose). If glucose were to fall to < 55 mg/dL, the following morning's clamp study would need to be postponed to a later date

because of the confounding influence of the counterregulatory response to hypoglycemia.

The PI will be physically present in the CRC for at least the first 3 overnight insulin infusions (T1DM or MODY2 subjects) to monitor and adjust the insulin infusion from the protocol if needed. Thereafter, the PI and CRC nurse manager will confer on the need for the PI (or a qualified M.D., N.P., or P.A.) to be physically present for the overnight insulin infusions based on the safety profile of the preceding IV insulin infusions. If the PI is not physically present, he will be readily available via telephone pager and will be within 20 minutes of the CRC.

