6.2.2.5 Rescheduling clamp study after a technical issue

It is possible once a clamp visit has begun a technical issue will prevent the successful completion of the study. For example, IV access may be lost during the study or otherwise uneventful hypoglycemia (glucose < 55 mg/dL) may occur for those participants receiving an overnight IV insulin infusion (section 6.2.2.1). In the event such a technical issue occurs, the PI may elect to reschedule a repeat clamp study with the following stipulations:

- A) The PI deems the technical issue poses no serious danger to the participant were it to occur again and the participant wishes to repeat the study
- B) The rescheduled clamp occurs within six months of the original screening visit
- C) An abbreviated screening procedure has been completed within one month of the repeated clamp visit. This abbreviated screening will re-assess inclusion/exclusion criteria (table 2) and safety to be restudied. The abbreviated screening will include:
 - Fasting blood tests: a complete metabolic panel (screening for hepatorenal disease), hemoglobin (screening for anemia), c-peptide, insulin, HbA1c, lipid panel
 - Urine pregnancy testing: on the night prior to the clamp in females

 History and Physical Exam: the participant's interval clinical history will be reviewed by the PI (or a designated KSP who is an M.D., Nurse Practitioner, or Physician's Assistant) on the evening prior to the clamp study and a physical exam will be performed. Anthropometric measurements will be repeated with the assistance of CRC staff or KSP.

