7.1 Exercise testing

During the screening visit, subjects will perform an exercise test to measure VO₂ max. Because inclusion/exclusion criteria dictate that the subjects will be young (ages 13-35), not obese (BMI 20-28), and those patients with diabetes will have relatively ideal glycemic control (HbA1c 6.0-8.0%), the risk of a cardiovascular complication of exercise is considered to be low. The greatest risk of the exercise test is hypoglycemia in the T1DM patients who will have been fasting overnight. The patient will be asked to check their capillary glucose using their home meter immediately prior to exercise and if glucose is < 100 mg/dL, they will consume 15 gm of glucose immediately prior to the \sim 10 minute exercise test. Immediately following this, all subjects will be provided with a meal, further minimizing exposure to hypoglycemia subsequent to the brief exercise test.

7.2 Hyperinsulinemia

Subjects will be exposed to hyperinsulinemia during the clamp study, which could lead to hypoglycemia and hypokalemia. We will implement the following to minimize these risks:

- As shown in figure 2, the highest insulin rate used will be 40 mU/m²/min. This is the most frequently applied insulin infusion rate in human hyperinsulinemic, euglycemic clamp studies.(53) This infusion rate is anticipated to result in plasma insulin concentrations between 50 and 130 μ U/mL, (54) levels that are within the range of physiological hyperinsulinemia and comparable to concentrations seen after meal ingestion. (53, 55, 56) By comparison, the most commonly used insulin infusion rate in the treatment of diabetic ketoacidosis is 0.1 U/kg/hr.(57) In a 70 kg, 1.73 m² individual, this infusion rate would equal 67 mU/m²/min, over 50% higher than the 40 mU/m²/min rate used in this study.
- Glucose will be monitored every hour during the overnight basal insulin infusion as outlined in 6.2.2.1. Glucose will be monitored every 5-10 minutes throughout the hyperinsulinemic clamp to guide the variable dextrose infusion and ensure euglycemia. Because glucose is monitored so frequently, a trend toward hypoglycemia would most likely be detected before hypoglycemia actually occurred. If hypoglycemia did occur, however, this frequent monitoring would allow for rapid detection of the low glucose concentration and rapid corrective treatment with an infusion of IV glucose (dextrose).

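### Section 8.0 keeps almost all study-induced hypoglycemia out of adverse event reporting, and no stated count of it reaches the safety monitor or the IRB

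*Combined protocol and SAP*

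**What the plan says.** Section 8.0 opens with a broad definition: "An AE will be considered to be any untoward medical occurrence in a subject", whether or not the study caused it. Its severity scale has room for non-serious events, for example "2 = Moderate: some limitation of usual activities, resolved with or without treatment". It then makes an exception for glucose: "Hypoglycemia and hyperglycemia will be reported as adverse events only in the case of requiring the assistance of others". The only reasons for assistance that it names are unconsciousness and DKA. Events that meet this test are classed as serious.

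Section 7.2 names hypoglycemia as a risk of the insulin given in the study ("which could lead to hypoglycemia and hypokalemia"). Section 6.2.2.1 gives T1DM and MODY2 subjects an overnight insulin infusion, and a value below 55 mg/dL during it postpones the clamp. Section 6.2.2.5 lists "otherwise uneventful hypoglycemia (glucose < 55 mg/dL") among its examples of technical problems after which the investigator may elect to reschedule.

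Section 8.0 also defines unanticipated problems. One criterion is that the event is "unexpected (in terms of nature, severity, or frequency"). The non-serious events that go into the annual report are the unanticipated ones only.

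**The concern.** Hypoglycemia is the foreseeable harm of the two study infusions, and the reporting rule skips every grade below loss of consciousness. A low that is treated at the bedside, or that cancels the next morning's clamp, is not graded as an adverse event. It also has no stated route to the people who oversee safety.

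Three parts of the protocol rely on that information:

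- Section 8.0 says annual IRB review should weigh risk as subjects actually experience it, and whether the protective measures are adequate.
- Section 7.6.2 argues that the risk to adolescents is a minor increase over minimal risk.
- The unanticipated-problem definition asks about frequency, but section 8.0 starts that assessment from an adverse event.

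If the commonest study-induced event is not an adverse event, oversight has no specified number to compare with expectation.

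**Working it through.** The plan states no figure to reproduce, because this is a reporting rule. The check has two parts: tracing what happens to a low, and sizing the number of lows.

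**Tracing a study-induced low**

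| Step | Where | What happens to a low without loss of consciousness |
|---|---|---|
| Measured | 6.2.2.1, 6.2.2.2, 6.2.2.4 | Yes: hourly overnight, every 5-10 min in the insulin periods, every 10 min for an hour afterwards |
| Acted on | 6.2.2.1, 6.2.2.5 | Yes: below 55 mg/dL overnight postpones the clamp; rescheduling is possible |
| Reviewed by the investigator | 8.0 | Yes for the post-study log, which is reported by subjects taking insulin |
| Graded as an adverse event | 8.0 | No, under the exception |
| Sent to the safety monitor or IRB as a count | 8.0 | No stated route: the listed reports cover unanticipated events and audit reports |

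**Inputs for scale**

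- Reference experience (6.2.2.1): 25 T1DM subjects. "Glucose fell to below 60 mg/dL on six occasions", and below 50 mg/dL on one occasion.
- Subjects infused overnight (10.0, group sizes): 16 T1DM + 10 MODY2 = 26.
- The timeline in 10.0 gives 18 + 12 = 30 subjects, against 10 + 16 + 10 = 36 from the group sizes. If 30 means 10 per group (an assumption), 20 are infused.

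**Expected occasions** = (reference occasions / 25) × subjects infused

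- Below 60: 6/25 = 0.24 per subject. 0.24 × 26 = 6.24; 0.24 × 20 = 4.8.
- Below 50: 1/25 = 0.04 per subject. 0.04 × 26 = 1.04; 0.04 × 20 = 0.8.

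**Chance of at least one** = 1 − (1 − rate)^n, taking at most one occasion per subject

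- Below 60, n = 26: 1 − 0.76^26 = 0.999.
- Below 50, n = 26: 1 − 0.96^26 = 0.654.

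**Adverse events under the current rule.** The documents give no rate for loss of consciousness. At an assumed 0.1% to 1% per infused subject:

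- Expected count: 26 × 0.001 = 0.03 to 26 × 0.01 = 0.26.
- Chance of any: 1 − 0.999^26 = 2.6% to 1 − 0.99^26 = 23%.

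**What a count could show (illustration only; exact binomial, 26 subjects)**

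- Flag at 11 or more subjects below 60: false-flag probability 3.0% at rate 0.24; 78% chance to detect a doubled rate of 0.48.
- Flag at 4 or more subjects below 50: false-flag probability 1.9% at rate 0.04; only 15% chance to detect a doubled rate of 0.08.

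A tally of milder lows can therefore detect a real excess in a study this small. A tally of deep lows mostly cannot, and a tally of losses of consciousness would be expected to stay at or near zero.

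**The case against.** The strongest reply is that this is a prespecified choice about an anticipated and closely watched event. The exception limits what is reported as an adverse event, not what is measured. No endpoint is affected. Much of this stands, and it rules out several stronger readings that a reader might draw:

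- *That these lows go unrecorded.* They do not. Glucose is measured throughout, and the investigator reviews post-study values and can alter the prevention procedure.
- *That the frequency criterion cannot be applied.* Section 8.0 defines an unanticipated problem as any incident, experience or outcome, which is wider than adverse events, and section 6.2.2.1 supplies a reference frequency. The criterion is usable in principle. It lacks a specified count, denominator and expected rate.
- *That the decision on overnight physician presence has no data behind it.* Section 6.2.2.1 rests it on the safety profile of earlier infusions, and hourly readings are available for that.
- *That every event short of loss of consciousness is exempt.* The important-medical-event criterion for SAEs, whose examples include seizures, could capture some. That sits badly with the word only in the exception, and the two need reconciling.
- *That MODY2 subjects take no insulin at home.* The documents do not say so, and Table 2 sets no such restriction.

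Two further objections shape the remedy. First, relabelling lows as adverse events would not by itself reach the annual report, since only unanticipated non-serious events go there and section 7.2 anticipates hypoglycemia. Second, home-log lows mix with background. Section 7.6.2 cites two episodes a week for the average T1DM patient, so 2/7 × 16 = about 4.6 would be expected in one day among 16 subjects, with no glucose threshold stated.

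The objection does not supply a route by which a count of milder in-unit lows reaches anyone outside the study team.

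**Conclusion.** The point holds as a gap in safety oversight. Study-induced hypoglycemia short of loss of consciousness is almost never reported as an adverse event, and no stated tabulation of it goes to the safety monitor or the IRB. The relevant volume is roughly 5 to 6 overnight occasions below 60 mg/dL and about 1 below 50, none of them an adverse event under the exception unless consciousness was lost.

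Those figures are for scale only. They assume that the T1DM reference rate carries over to this study and to MODY2 subjects, who retain insulin secretion (section 2.0). The source counts occasions, not subjects, and section 6.2.2.1 here also allows preventive dextrose below 75 mg/dL. No rate is given for below 55; at the reference rates the count would lie between the two. The clamp itself is not in these numbers.

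The primary and secondary outcomes are unaffected. The change is worth making because it is cheap and uses data already collected, in a study that enrols adolescents from age 13.

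**What to change.** In section 8.0, keep the SAE rule and the exemption for everyday outpatient hypoglycemia, and add the following:

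1. **Record** as a non-serious study-related event any glucose below 55 mg/dL (the protocol's own postponement limit), or any dextrose given to treat a low, during the overnight infusion, the clamp and the monitored hour after it. Do not count the planned clamp glucose infusion or the preventive dextrose in section 6.2.2.1.
2. **Tabulate** by phase and by group, giving both occasions and subjects affected, with the number infused as denominator. Phases need separate rows because sampling is hourly overnight and every 5-10 min in the clamp.
3. **Send** the table to the safety monitor and the IRB. This step is essential, because the existing route forwards only unanticipated events. State the expected rate against which frequency will be judged.
4. **List 24-hour home-log lows separately.** They include background episodes, and only subjects taking insulin report the log.
5. **Reconcile** the word only in the glucose exception with the important-medical-event criterion for SAEs, and the 36 and 30 totals in section 10.0, which set the denominator.

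The cost is a few case-report lines and a longer safety report. Nothing changes in how subjects are monitored or treated.
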